2.6.2 Clinical Data

Tumor-treating fields (TTFields) are approved for use in patients with glioblastomas at recurrence (2011) or adjuvant setting (2016) due to overall survival benefit in various trials. In the EF11 study for recurrent glioblastoma, TTFields monotherapy showed a response rate of 14% compared to <5% response for any salvage therapy as per physician preference, including CCNU, bevacizumab, etc. (Stupp et al, Eur J Cancer 2012). The phase III (EF-14) trial for newly diagnosed glioblastoma also revealed an increase in median survival from 19.8 to 24.5 months for patients treated with adjuvant TTFields and temozolomide versus temozolomide alone.

Given preliminary preclinical data demonstrating synergy between TTFields and checkpoint immunotherapy, the rates and outcomes of combination TTFields and immunotherapy were analyzed in a retrospective gliomas cohort (Odia et al, Posters: SNO 2016 and AACR 2017; Schulte et al, SNO 2017).

Since 12/2012, 52 patients with newly diagnosed or recurrent gliomas were treated with TTFields therapy at Columbia University. Of 52 treated patients, 21 (40%) were women and 3 (6%), 5 (10%) and 43 (84%) had WHO grade II, III and IV gliomas, respectively. Median age at diagnosis was 58 (23-84) years. TTFields therapy was used at recurrence in 42 (81%), with a range of 0-4 prior recurrences. Prior therapies included bevacizumab (21, 20%), resection [gross total in 28 (54%)], radiation [mainly 60 Gy in 30 fractions, 44 (85%)] and temozolomide (100%). Median duration of TTFields therapy was 2.4 (0.1-20.3) months. Eleven (21%) patients met the TTFields compliance goal of 75%. Concurrent systemic therapy was used in 40 (77%), including

temozolomide (16, 31%), nitrosourea (4, 8%), bevacizumab (19, 37%), or checkpoint immunotherapy (28, 54%). Nivolumab was the predominant immunotherapy used and dosed 240 mg every 2 weeks. Only 2 (4%) experienced skin toxicity requiring TTFields therapy interruption.

Progression free (PFS) and overall (OS) survival among all patients was 3.6 and 21.5 months, respectively. Median PFS was significantly increased among glioblastoma patients treated with concurrent immunotherapy (4.6 vs. 3.5 months, p=0.04). There was a trend toward increased overall survival after TTFields therapy with addition of immunotherapy (8.3 vs. 6.5 months, p=0.32).

Objective response rate (ORR: defined as complete response, partial response or stable disease for 6 months) based on RANO was increased in patients treated with concurrent immunotherapy versus all other antineoplastic therapy (26% vs. 13%). This is greater than the 14% reported in the phase II EF-11 trial of NovoTTF100A monotherapy (Stupp et al, Eur J Cancer 2012) or the <5-10% objective response seen for early phase trials of checkpoint inhibitor monotherapy, including nivolumab, for recurrent glioblastoma (Preusser et al, Nat Rev Neurol 2015).

Example of Radiographic Response

A patient with recurrent glioblastoma experienced clinical improvement and marked partial response on combination NovoTTF200A (OptuneTM) and nivolumab. Pretreatment post-gadolinium T1 (A) and T2 (B) compared to post-treatment post-gadolinium T1 (C) and T2 (D) are shown.

TTFields therapy improves survival for patients with glioblastomas. Immunotherapy also shows promise in various neoplasms. The possible synergism between these modalities in preclinical studies and the retrospective glioma series warrants further study as proposed.

2.6.3 Rationale for dose schedule

A phase I trial of nivolumab 1 mg/kg plus ipilimumab 3 mg/kg every 3 weeks for 4 doses followed by maintenance nivolumab 3 mg/kg every 2 weeks revealed tolerable immune-related

toxicity profiles among patients with recurrent glioblastoma and comparable to other tumor types (Sampson J, et al. ASCO 2015: CHECKMATE-143 (NCT02017717) glioblastoma arm). The most common causes of discontinuation were AEs: diarrhea, alanine aminotransferase (ALT) increased, aspartate aminotransferase (AST) increased, lipase increased, diabetic ketoacidosis, hypocalcemia, hypomagnesemia, hyperthyroidism, cholecystitis, and sepsis.

Another multi-cohort phase 3b/4 trial assessed the efficacy of nivolumab IV 240 mg every 2 weeks plus a maximum of 4 doses of ipilimumab IV 1 mg/kg every 6 weeks followed by maintenance nivolumab for a maximum of 24 months in patients with stage IIIb to IV non-small cell lung cancer (NSCLC), newly diagnosed or recurrent after platinum-based therapy (Pillai RN, et al. AACR 2017: CHECKMATE-817 (NCT02869789)). The study revealed a tolerable toxicity profile comparable to monotherapy profiles, with discontinuation rates of 12% for any grade or grade 3-4 treatment related toxicities. Objective response rates (ORR) were improved for the combination of nivolumab and ipilimumab compared to nivolumab monotherapy. Efficacy measures were comparable to more intense dosing regimens.

with other agents in chemotherapy-naïve patients with NSCLC The combination of nivolumab (3 mg/kg) every 2 weeks (Q2W) plus ipilimumab (1 mg/kg) every 12 or 6 weeks (Q12W or Q6W) showed promising efficacy. Nivolumab in combination with ipilimumab was well

tolerated and treatment-related adverse events (TRAEs) were consistent with the known safety profiles of the individual agents. The discontinuation rates attributable to TRAEs in the nivolumab plus ipilimumab cohorts were similar to nivolumab monotherapy (12% for any grade and 12% for grade 3/4). No treatment-related deaths occurred at the time of analysis.

The combination of nivolumab (3 mg/kg) every 2 weeks plus ipilimumab (1 mg/kg) every 6 weeks as the proposed has been well-tolerated, while nivolumab is approved and proven safe as monotherapy when dosed as 240 mg every 2 weeks. Hence, this study utilizes distinct dosing schedules for nivolumab when dosed as monotherapy versus in combination with ipilimumab based on approved and proven safe dosing.

2.7 **Correlative Studies Background**

^aResponse per investigator assessment

Archival tumor tissue will be collected to evaluate molecular predictors of outcome such as MGMT promoter methylation, PDL-1 tumor expression, and tumor mutational load as per available funding.

3. PARTICIPANT SELECTION

3.1 Eligibility Criteria

- 1. Male or female patients with age ≥ 18 years.
- 2. Histologically confirmed World Health Organization Grade IV glioblastoma with supratentorial distribution.
- 3. Unequivocal evidence of progressive disease on contrast-enhanced brain CT or MRI as defined by RANO criteria, or documented recurrent glioblastoma on biopsy.
- 4. Measurable disease based on RANO criteria.
- 5. Prior therapies including radiation and temozolomide.
- 6. Any number of recurrences are allowed. Resection of recurrent glioblastoma is not considered a prior treatment.
- 7. From the projected start of study treatment, the following periods must have elapsed: 4 weeks from any investigational agent, 4 weeks from cytotoxic therapy (except 23 days for temozolomide and 6 weeks from nitrosoureas), or 4 weeks from any other antibodies or any other antineoplastic therapies.
- 8. Must be at least 12 weeks from radiotherapy or progression outside of the high-dose radiation target volume or unequivocal evidence of progressive tumor on biopsy.
- 9. All adverse events Grade > 1 related to prior therapies (chemotherapy, radiotherapy, and/or surgery) must be resolved, except for alopecia.
- 10. Karnofsky Performance Status (KPS) \geq 60 (see Appendix A).
- 11. Adequate organ and marrow function as defined below, all screening labs should be performed within 14 days of treatment initiation:

•	absolute neutrophil count	\geq 1,000/mcL
•	platelets	\geq 100,000/mcL
•	hemoglobin	> 8.0 mg/dL
•	total bilirubin	\leq 2.0 x upper limit of normal
•	AST (SGOT)/ALT (SGPT)	$\leq 2.5 \times$ upper limit of normal
•	creatinine or creatinine clearance	\geq 60 mL/min/1.73 m ² for creatinine >ULN

- 12. Corticosteroid dose must be stable or decreasing for at least 5 days prior to enrollment.
- 13. Nivolumab and ipilimumab are potentially teratogenic or abortifacient. Women of childbearing potential and men must agree to use adequate contraception (hormonal or barrier method of birth control; abstinence) prior to entry and for the duration of study. Should a woman become pregnant or suspect she is pregnant while she or her partner is participating in this study, she should inform her treating physician immediately. Male subjects should agree to use adequate method of contraception starting with the first dose through 7 months after the last dose of therapy.

- 14. Brain CT or MRI within 14 days prior to start of study drug.
- 15. Archival tissue for evaluation of correlative objectives (if available).
- 16. Ability to understand and the willingness to provide written informed consent.

3.2 Exclusion Criteria

- 1. Infratentorial disease
- 2. Bevacizumab within 2 months of enrollment. Prior use of ipilimumab or other CTLA-4 inhibitor or prior TTFields.
- 3. Tumors with known *IDH1* (isocitrate dehydrogenase 1) or *IDH2* mutations as determined by immunohistochemistry for the *IDH1* R132H variant or by direct sequencing. *IDH1/2*-mutant gliomas have a prolonged overall survival rate compared to *IDH1/2*-wildtype gliomas (Parsons et al., 2008; Yan et al., 2009), indicating distinct natural history.
- 4. History of allergic reactions attributed to compounds of similar chemical or biologic composition to nivolumab or ipilimumab or their excipients.
- 5. Current or planned participation in a study of an investigational agent or using an investigational device.
- 6. Uncontrolled intercurrent illness including, but not limited to, ongoing or active infection or psychiatric illness/social situations that would limit compliance with study requirements.
- 7. Active or life-threatening infection requiring intravenous or >2 weeks of systemic therapy.
- 8. Prior stereotactic radiotherapy, convection enhanced delivery (CED) or brachytherapy requires a biopsy to confirm radiographic progression is consistent with progressive tumor and not treatment-related necrosis unless the recurrent lesion is outside of any prior high-dose radiation target volume or distant from the prior CED or brachytherapy site.
- 9. There is an unknown but potential risk for adverse events in nursing infants secondary to treatment of the mother with these agents, so breastfeeding must be discontinued by enrollment on study.
- 10. Uncontrolled HIV or AIDS is not allowed. Patients with known history of HIV but with undetectable viral load on antiretroviral therapy are allowed.
- 11. CHF, or MI or hemorrhagic/ischemic stroke in the last 3 months
- 12. Active illicit drug use or diagnosis of alcoholism
- 13. Known additional malignancy that is progressing or requires active treatment within 3 years of start of study drug. Exceptions include basal cell carcinoma of the skin, squamous cell carcinoma of the skin, *in situ* cervical cancer or other *in situ* malignancy that has undergone potentially curative therapy and/or with >90% probability of survival beyond 5 years.
- 14. Any surgery (not including minor diagnostic procedures such as lymph node biopsy) within 2 weeks of start of treatment. Incomplete recovery from any side effects of previous procedures

is also exclusionary.

- 15. Any significant autoimmune disorders expected to impact multiple or internal organs, excluding mild eczema or autoimmune thyroiditis treated with thyroidectomy and requiring systemic immunosuppressive or immunomodulatory therapy.
- 16. Any implanted programmable cranial device, including reprogrammable ventriculoperitoneal shunt (VPS) or cochlear implants, that precludes use of TTFields (Optune) therapy.

3.3 Inclusion of Women and Minorities

Both men and women of all races and ethnic groups are eligible for this trial.

4. REGISTRATION PROCEDURES

Each institution will register eligible participants per local registration procedures. The investigator is responsible for enrolling only those patients who have met all eligibility criteria.

5. TREATMENT PLAN

5.1 Study Design

This is an open-label Phase II trial with two parallel arms, two-stage design with appropriate stopping rules for poor efficacy. Arm A will enroll patients without prior history of any PD1/PDL1 checkpoint inhibitor, while Arm B will enroll patients with prior PD1/PDL1 checkpoint inhibitor. We expect to enroll at least 30 (15 in each Arm) and a maximum of 60 (30 in each Arm) evaluable subjects on this study. The study schema is depicted below.

NovoTTF200A (Optune) is a device to be worn continuously for a goal of \geq 75% of the time, ranging from 18 hours daily nonstop or 22 hours daily with 2-3 days off monthly. Patients will be encouraged to meet compliance goals via timely feedback and troubleshooting concerns. TTFields therapy begins once approved by insurance and an in-home initiation visit scheduled. The goal is to start within 1 month of starting immunotherapy infusions. Treatment is planned for ~24 months.

Infusions will start within 14 days of sreening/baseline visits. Nivolumab will be dosed every 2 weeks IV 240 mg as monotherapy and 3 mg/kg with ipilimumab. Nivolumab will not exceed 48 doses (24 months). Ipilimumab starts with the second infusion of nivolumab for Arm B (prior immunotherapy) or after progression on single agent nivolumab for Arm A (no prior immunotherapy). Ipilimumab infusions will be dosed as 1 mg/kg once every 6 weeks for a maximum of 4 doses (24 weeks).

Infusions will continue until maximum duration of ipilimumab and nivolumab therapy or when there is confirmed tumor progression, death, intolerable adverse effects or withdrawal. After the maximum of 24 months of therapy, clinical, radiographic and quality of life assessments are performed every 8 weeks until or when there is confirmed tumor progression, death, or withdrawal. One treatment cycle is defined as 6 weeks for the initial 24 months, thereafter every 8 weeks will define observation cycles.

Reported adverse events and potential risks are described in Section 7. Dose modifications are described in Section 6. No investigational or commercial agents or therapies other than those described below may be administered with the intent to treat the participant's malignancy.

5.2 **Pre-Treatment Criteria**

All patients must sign an informed consent prior to any study-specific procedure. For screening, patients will have the following tests done at the treating institution or in a local lab within 14 days of treatment initiation:

Hematology Panel	Blood Chemistry Panel	Others
ANC	AST (SGOT)	Pregnancy test (blood)
Platelet count	ALT (SGPT)	Urine analysis
Hematocrit	Creatinine and BUN	PT, PTT, INR
Hemoglobin	Total/direct bilirubin	TSH and free T4
RBC	Alkaline phosphatase	LDH
WBC with differential	Calcium	ACTH
	Magnesium	
	Phosphate	
	Potassium	
	Sodium	
	Random glucose	
	Total protein and Albumin	

Hematologic lab values should be re-evaluated on cycle 1 day 1 and need to meet eligibility parameters to start treatment.

Patients will undergo complete history, including concomitant medications, physical examination, measurement of vital signs (pulse, sitting or supine blood pressure, respiratory rate, temperature) and weight, and clinical assessment of Karnofsky performance status (KPS). Patients must have had a contrast-enhanced brain MRI or CT scan within 14 days of starting study drug. Measurable disease is required for enrollment.

5.3 Treatment and Evaluation/ Observation Cycles

Blood draws are also performed within 2 days of each infusion. Screening/ Baseline lab results may be used for C1D1 if performed within 14 days of initial treatment. Hematology and blood chemistry panel results must be reviewed by an investigator prior to each infusion. After the maximum of 24 months of therapy, blood draws will only be performed with every clinical and radiographic assessment every 8 weeks.

Prior to each infusion every 2-3 weeks and beyond the initial 24 months every 8 weeks, patients will undergo physical examination, neurological exam, and KPS assessment. Response assessment by MRI or CT and FACT-BR quality of life questionnaires will be performed every 6 weeks for the initial 24 months of therapy and thereafter every 8 weeks. Targeted questioning will collect adverse events and concomitant medications.

To confirm objective response (OR), partial or complete response (see section 11.1 for definitions) by tumor measurements must be confirmed by repeat assessments performed ≥ 4 weeks after the criteria for response are first met. Progression should also be confirmed by repeat scans ≥ 4 weeks after progression first suspected on MRI or CT.

If the participant undergoes another surgery for presumed tumor progression, but pathological findings are consistent with pseudoprogression, the participant will be deemed to not have had tumor progression and may continue treatment with nivolumab after principal investigator review.

5.4 End of Treatment Visit

For patients who come off study for toxicity or withdrawal of consent, tumor imaging is at the judgment of the investigator, suggested every 8-12 weeks in the appropriate setting after termination of the study therapy.

If patients come off treatment for progression of disease (Arm B only), intolerance, or withdrawal, they will be seen for assessments of efficacy and safety.

Patients will have repeat safety labs, a clinical examination, weight and KPS assessments, and concurrent medications within 30 days of the last infusion.

If tumor assessments are not done within 4 weeks, these will be obtained within the next 2 weeks after the End of Treatment Visit. After the end of treatment, each subject will be followed for 30 days for adverse event monitoring and 100 days for serious adverse event reporting. Participants removed from protocol therapy for unacceptable adverse events (Section 7) will be followed until resolution or stabilization of the adverse event.

Subjects who discontinue for reasons other than progressive disease will have post-treatment

follow-up for disease status until disease progression, initiating a non-study cancer treatment, withdrawing consent or becoming lost to follow-up. Subjects will be followed for survival every 2-3 months for a minimum of 1 year, or indefinitely until death or loss to follow-up.

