5.10 Criteria for Taking a Participant Off Study

Participants will be removed from study when any of the following apply: lost to follow-up, withdrawal of consent, or death. The reason for taking a participant off study, and date the participant was removed, must be documented in the case report form (CRF).

Severe adverse events, availability of new adverse toxicology in animals, and financial difficulties due to withdrawal of funds may result in stopping the trial. The investigator or IRB may take such actions. If the trial is terminated for safety reasons, subjects will be notified immediately and assured that appropriate treatment and follow-up will be available. If an investigator terminates the trial, the investigator will inform the subjects and IRB about the reason for such action. Similar notifications will be sent by the IRB if it takes such an action.

The reason for taking a participant off study, and the date the participant was removed, must be documented in the clinical source documentation.

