13.2 Definitions

Evaluable: All study-eligible patients who receive at least one infusion of nivolumab will be considered *evaluable for safety and toxicity*. To be *evaluable for efficacy*, patients must be study eligible, receive at least one cycle (6 weeks) of immunotherapy and complete initial disease assessment at ≥ 6 weeks after starting therapy.

Exclusions: Any patient who is enrolled on study, but does not receive any component of study treatment, will be excluded from all efficacy analyses. Any patient who initiates treatment and is later found to be ineligible for study (e.g., protocol violation) will be withdrawn from study but will be followed for disease progression, toxicity and survival. The experience of such patients will be characterized separately from that of evaluable patients. Reasons for exclusion of enrolled patients from the analysis set for efficacy, or for safety, will be characterized.

Overall response rate (ORR): Overall response rate is the proportion of patients whose best overall response per modified iRANO criteria or standard RANO criteria is complete (CR) or partial (PR) after at least 6 weeks from start of therapy. iRANO additionally requires best overall response of CR or PR to be sustained, that is, confirmed by a second assessment at \geq 4 weeks later. Patients who clinically progress before the initial radiographic assessment after 1 cycle (6 weeks) will be considered nonresponders.

Progression-free survival (PFS): PFS will be measured from the start date of treatment until

documented evidence of disease progression, clinical progression or death from any cause, after at least 8 weeks from start of therapy. Radiographic progression should be confirmed by a second assessment at \geq 4 weeks later. For patients who remain alive without progression, follow up time will be censored at the date of last assessment.

Overall survival (OS): Survival will be measured from the start date of treatment to the date of death from any cause or last contact (censored observations).

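### The PFS rules treat a patient who starts non-study cancer treatment before progression according to later survival: censored if alive, an event at the date of death if dead

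*Combined protocol and SAP*

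**What the plan says.** Four places in the combined protocol and SAP bear on this.

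- **Section 5.4 (End of Treatment Visit).** Patients who stop study treatment without progression are given "follow-up for disease status until disease progression, initiating a non-study cancer treatment, withdrawing consent or becoming lost to follow-up". Survival has its own, longer schedule: "Subjects will be followed for survival every 2-3 months for a minimum of 1 year, or indefinitely until death or loss to follow-up".
- **Section 5.10.** Starting another treatment does not take a patient off study: "Participants will be removed from study when any of the following apply: lost to follow-up, withdrawal of consent, or death". Deaths after a switch are therefore captured.
- **Section 13.2.** A PFS event is "documented evidence of disease progression, clinical progression or death from any cause". The only PFS censoring rule is "For patients who remain alive without progression, follow up time will be censored at the date of last assessment". OS, by contrast, runs to "death from any cause or last contact (censored observations").
- **Section 10 (study calendar).** The follow-up column has a row for disease status and survival. The matching footnote describes telephone contact every 2 to 3 months for all subjects and does not stop at new treatment. The footnote numbers are off by one against the table, but only this note fits the row.

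Section 13.4 plans Kaplan-Meier estimates of PFS at 6 and 12 months. Neither 13.2 nor 13.4 mentions non-study cancer treatment, limits the gap between the last scan and a death, or plans a sensitivity analysis for PFS.

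**The concern.** There are two usual ways to handle a new cancer treatment started before progression: censor at the last assessment before it, or count it as an event. Each can be defended. The rules as written do neither consistently, because the handling depends on whether the patient later dies.

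This matters for Kaplan-Meier, which needs the decision to censor to be independent of what happens afterwards. Here a switcher who dies is kept at risk, and counted as progression-free, through a period in which section 5.4 requires no disease follow-up. A switcher who survives leaves the risk set when the scans stop.

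PFS at 6 and 12 months is a reported secondary result. Without a randomised control arm, it can be read only against figures from other studies, so the rule behind it has to be stated and consistent.

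**Working it through.** **No plan figure to reproduce.** The documents give no target, event count or power for PFS. The check is a reading of the rules, followed by an illustration of size.

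**1. The rules applied to two patients.** Both stop for toxicity, have their last scan at month 3 and then start non-study treatment.
- Alive at the data cut: censored at month 3.
- Dead at month 10: event at month 10. The 10 − 3 = 7 months without scheduled scans count as progression-free, unless progression is picked up some other way.

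This takes the last assessment in 13.2 to be a disease assessment, which the contrast with last contact for OS supports. If it meant a survival call, living patients would also gain unobserved progression-free time.

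**2. Inputs for the illustration.**
- Median PFS 4.6 months and median OS 8.3 months, from the retrospective TTFields-plus-immunotherapy patients in section 2.6.2.
- Follow-up uniform over 12 to 36 months, from section 13.3 (accrual within two years, then at least one year).
- Share switching before progression: not in the documents. Assumed 5% to 25%, with switch times between months 1.5 and 5, unrelated to prognosis.
- Exponential time to progression, and exponential survival after progression with median 8.3 − 4.6 = 3.7 months.
- No progression recorded after a switch (the literal reading of 5.4).

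**3. True values.** S(t) = 2^(−t/4.6).
- S(6) = 2^(−1.304) = 40.5%
- S(12) = 2^(−2.609) = 16.4%

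**4. Kaplan-Meier in large simulated samples.**

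| Handling of switchers | 6-month PFS | 12-month PFS |
|---|---|---|
| Scans continued to progression | 40.5% | 16.4% |
| As written, 5% to 25% switching | 41.4% to 45.6% | about 17% to 21% |
| Censored at the switch, dead or alive | about 40.5% | about 16.4% |

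The rule as written therefore adds about 1 to 5 points at each time.

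**5. Other assumptions.**
- Switch times spread over the whole period before progression, 10% / 20% / 30% switching: 6-month PFS 41.7% / 43.4% / 45.1%, median 4.7 / 4.9 / 5.2 months.
- The same with a median PFS of 3.6 months (the whole retrospective cohort): true 6-month PFS of about 31.5% becomes 33.4% / 35.6% / 38.3%.
- Subtracting medians does not return the 8.3-month OS. The model in step 2 has a median OS of about 10.0 months. Shortening post-progression survival to a median of about 2.4 months restores 8.3, and the ranges in step 4 become about 41.3% to 45.0% at 6 months and 16.9% to 19.0% at 12 months.

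**6. If switching is related to prognosis.** Suppose about one patient in five starts other treatment shortly before progression would have been recorded. Against a true 6-month PFS of 40.5%, the written rule gives 46.8%, censoring at the switch 47.6%, and counting the switch as an event 39.7%. When switching is unrelated to prognosis the order is different: censoring is right, and counting the switch as an event is too low (36.7% / 32.4% / 27.5% at 10% / 20% / 30% switching).

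**The case against.** **The affected group is narrow, and its size is assumed.** This stands. The patient must stop without progression and then switch before any progression is recorded. Clinical progression is already an event in 13.2, and section 11.3.3 counts failure to return because of death or deterioration as progression. Section 11.1 replaces patients who stop before response assessment for other reasons. The calendar keeps toxicity discontinuers on 8-weekly scans in the observation phase. The one discontinuation rate in the documents is 12%, in a lung-cancer study (section 2.6.3), and not all such patients would switch before progressing. That is why the range above starts at 5%.

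**The effect is small against sampling error.** This also stands. With 30 patients in an arm and S = 0.40, the standard error of log(−log S) is √[0.6/(30 × 0.4)] / |ln 0.4| = 0.2236/0.9163 = 0.244. The 95% limits are 0.4^exp(±1.96 × 0.244), or about 23% to 57%. The bias, however, would not shrink with more patients.

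**Censoring at the switch is not always better.** This stands. Step 6 shows it slightly further from the truth than the written rule when worsening patients switch. The sensitivity analysis is therefore part of the fix.

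A reader might also infer two stronger points that the documents do not support:

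- **That progression after a switch is never looked for.** The calendar provides telephone follow-up of disease status for all subjects, and clinical progression counts as an event. Some progressions may be found this way. What is missing is scheduled scans, and agreement between 5.4 and the calendar.
- **That the bias changes direction as the data mature.** If every patient were cut at 12 months, the same model would report 12-month PFS as 14.7%, 13.7% or 12.7% (12%, 19% or 25% switching) against 16.3%. Section 13.3 plans no such cut. With 12 to 36 months of follow-up the bias is upward at both times.

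**Conclusion.** The inconsistency is real and follows from reading 5.4 and 13.2 together. PFS handling of a patient who starts non-study treatment before progression depends on later death, which matches neither standard rule.

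Under the planned follow-up the effect is an overstatement. In the main illustration it is about 1 to 5 points on PFS at both 6 and 12 months, for 5% to 25% switching unrelated to prognosis. That size rests on assumed switching shares, exponential times and no progression recorded after the switch. Telephone follow-up would reduce it. It could be larger if worsening patients switch.

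The consequence is confined to a descriptive secondary endpoint. The primary ORR, the futility rule and the final decision rule do not use PFS. The change is still worth making, because it is cheap and should be settled before the data are seen.

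**What to change.** 1. In section 13.2, state that a patient who starts non-study cancer treatment before progression is censored for PFS at the last disease assessment before that treatment, whether or not death follows.
2. Add one sensitivity analysis that counts the start of non-study treatment as a PFS event. Under the two switching patterns examined, the two estimates bracket the truth: censoring is right when switching is unrelated to prognosis, and the event version is close when patients switch just before progression.
3. Align section 5.4 with the calendar's follow-up row, so that it is clear whether and how disease status is collected after non-study treatment starts.

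The cost is two sentences in 13.2, one consistency edit between 5.4 and the calendar, and one extra Kaplan-Meier run. The main analysis has slightly fewer PFS events, because deaths after a switch no longer count there; they remain in OS. No additional patients or scans are needed.
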